8.3 Vital Signs

Vital signs measurements will include body temperature, systolic blood pressure (SBP), diastolic blood pressure (DBP), and heart rate. Blood pressure (ie, SBP, DBP) and heart rate will be measured in the supine and standing positions. Measurements at different positions will be treated as different parameters for purposes of data analysis. Thus, there will be 7 parameters for the vital signs.

The assessment value and the change from baseline value in each of the 7 vital signs parameters during the open-label treatment period will be summarized by visit on the OC data by using descriptive statistics for continuous variables. Likewise, the summary statistics will be computed for the last assessment visit based on the LOCF data.

Potentially clinically relevant vital signs abnormalities during the open-label treatment period will be identified, and the number and percentage of subjects who had such an abnormality in each of the vital signs will be tabulated by prior treatment group based on the observation from the scheduled and the unscheduled (if any) post-baseline visits.

All potentially clinically significant vital signs abnormalities will be listed by prior treatment group, patient ID, baseline value, age, sex, body weight, visit week, type of visit (virtual or in office), and dose at onset of the event if applicable.

Criteria for Identifying Vital Signs of Potential Clinical Relevance for subjects 5 to 17 years of age are provided in Appendix 1.

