### 3.5 Endpoints

### 3.5.1 Primary Endpoint

Safety will be assessed by the following standard endpoints for clinical trials and trials of antipsychotic drugs:

- The frequency and severity of adverse events (AEs), serious AEs (SAEs), and discontinuation from the trial due to AEs.
- Change from baseline to postbaseline time points in 1) vital sign measurements, 2) electrocardiogram (ECG) parameters, 3) clinical laboratory tests (including prolactin) and urinalysis, and 4) physical examination findings.
- Analysis of potential suicide events recorded on the Columbia-Suicide Severity Rating Scale (C-SSRS).
- Changes from baseline to postbaseline time points in results from EPS scales (Simpson Angus Scale [SAS], Abnormal Involuntary Movement Scale [AIMS], and Barnes Akathisia Rating Scale [BARS]).
- Percentage of subjects with clinically significant changes in weight (gain or loss) from baseline to specified time points.
- Time to discontinuation.

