#### 3.7.3.3.2 Vital Signs

Vital sign measurements will include body weight (measured at baseline, Week 14, and Week 26), body temperature, systolic blood pressure (SBP), diastolic blood pressure (DBP), and heart rate. The following guidelines will aid in the standardization of body weight measurements:

- The same scale should be used to weigh a given subject each time, if possible.
- Scales should be calibrated and reliable; scales should be at zero just prior to each subject's weigh-in session.

- A subject should void prior to being weighed and be minimally clothed (ie, no shoes or heavy overgarments).
- Weight should be recorded before a subject's meal and at approximately the same time at each visit.

Blood pressure and heart rate measurements will be made in the supine and standing positions after the subject has been in each position for at least 3 minutes. The supine measurements will be performed first, followed by standing. At the in-clinic visits, equipment at the site will be used for the measurements. For the virtual visits, equipment will be provided to the caregiver with instructions for home use. The results of these tests must be reviewed by the investigator in order to determine if any results are considered to be clinically significant.

Subjects should be excluded if they have any vital sign measurement at screening that, in the investigator's judgment, is medically significant in that it would impact the safety of the subject or the interpretation of the trial results. However, any abnormal screening vital sign result(s) considered to be clinically significant may be repeated once to confirm the finding(s) before excluding the subject from the trial. Appendix 1 is included to assist investigators in their assessments of results that may be potentially medically significant, depending on the subject's medical history and clinical presentation.

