- CT-9.1 Listing of Deaths (Safety Sample)
- CT-9.2 Listing of Serious Adverse Events (Safety Sample)
- CT-9.3 Listing of Discontinuations from Study Medication Due to Adverse Events (Safety Sample)
- CT-10.1 Criteria for Laboratory Test Values with Potentially Clinical Relevance
- CT-10.2.1 Listing of Laboratory Test Values with Potentially Clinical Relevance by Subject (Safety Sample)
- CT-10.2.2 Listing of Laboratory Test Values with Potentially Clinical Relevance by Test (Safety Sample)
- CT-10.2.3 Incidence of Laboratory Test Values with Potentially Clinical Relevance (Safety Sample)
- CT-10.3.1 Summary of Change from Baseline in Clinical Laboratory Test Results Serum Chemistry (Safety Sample)

[figure not shown]
- CT-10.3.2 Summary of Change from Baseline in Clinical Laboratory Test Results Hematology (Safety Sample)
- CT-10.3.3 Summary of Change from Baseline in Clinical Laboratory Test Results Urinalysis (Safety Sample)
- CT-10.3.4 Summary of Change from in Clinical Laboratory Test Results Prolactin, by Sex (Safety Sample)
- CT-10.3.5 Summary of Change from in Clinical Laboratory Test Results Other Tests (Safety Sample)
- CT-10.4.1 Shift Tables of Clinical Laboratory Test Results Serum Chemistry (Safety Sample)
- CT-10.4.2 Shift Tables of Clinical Laboratory Test Results Hematology (Safety Sample)
- CT-10.4.3 Shift Tables of Clinical Laboratory Test Results Urinalysis (Safety Sample)
- CT-10.4.4 Shift Tables of Clinical Laboratory Test Results Prolactin (Safety Sample)
- CT-10.5.1 Incidence of Potential Serious Hepatotoxicity (Safety Sample)
- CT-10.5.2 Listing of Potential Serious Hepatotoxicity (Safety Sample)
- CT-10.6.1 Incidence of Laboratory Test Values with Potential Clinical Relevance Serum Prolactin (Safety Sample)
- CT-10.6.2 Listing of Laboratory Test Values with Potential Clinical Relevance Serum Prolactin (Safety Sample)
- CT-11.1 Criteria for Potentially Clinically Relevant Abnormalities in Vital Signs
- CT-11.2.1 Listing of Potentially Clinically Relevant Abnormalities in Vital Signs (Safety Sample)
- CT-11.2.2 Incidence of Potentially Clinically Relevant Abnormalities in Vital Signs (Safety Sample)
- CT-11.2.3 Summary of Change from Baseline in Vital Signs by Visit (Safety Sample)
- CT-12.1.1 Criteria for Potentially Clinically Relevant Abnormalities in ECG Evaluations
- CT-12.1.2 ECG Diagnosis Mapping for Potentially Clinically Relevant Electrocardiogram Abnormalities (Safety Sample)

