Appendix 1 Criteria for Identifying Vital Signs Outside of Normal Values and of Potential Clinical Relevance

| Variable | Criterion Value | Change Relative to Baseline |
|--------------------------|-------------------------|-----------------------------------|
| Heart Rate at Rest | < 60 bpm or > 110 bpm | Increase or decrease of ≥ 15 bpm |
| | | |
| Systolic Blood Pressure | | |
| Preschooler (5 y) | < 80 mmHg or > 115 mmHg | Increase or decrease of ≥ 20 mmHg |
| School-age (6-9 y) | < 85 mmHg or > 115 mmHg | Increase or decrease of ≥ 20 mmHg |
| Preadolescent (10-12 y) | < 90 mmHg or > 120 mmHg | Increase or decrease of ≥ 15 mmHg |
| Adolescent (13-17 y) | < 90 mmHg or > 120 mmHg | Increase or decrease of ≥ 15 mmHg |
| | | |
| Diastolic Blood Pressure | | |
| Preschooler (5 y) | < 45 mmHg or > 80 mmHg | Increase or decrease of ≥ 15 mmHg |
| School-age (6-9 y) | < 50 mmHg or > 80 mmHg | Increase or decrease of ≥ 15 mmHg |
| Preadolescent (10-12 y) | < 60 mmHg or > 80 mmHg | Increase or decrease of ≥ 15 mmHg |
| Adolescent ≥ 13 y | < 60 mmHg or > 85 mmHg | Increase or decrease of ≥ 15 mmHg |

The criterion value and change relative to baseline represented in this table are intended to identify ontreatment values outside of normal changes and that could potentially be clinically relevant. In order to be identified as potentially clinically relevant, the on-treatment value must meet the "Criterion Value" and also represent a change from the subject's baseline value of at least the magnitude shown in the "Change Relative to Baseline" column. When evaluating these values, the emotional state of the subject must be taken into consideration (eg, crying, screaming) and documented as applicable.

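### Blood pressure and heart rate are taken lying and then standing at every visit, but no planned output counts subjects whose pressure falls on standing

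*SAP*

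**What the plan says.** Protocol 3.7.3.3.2 has blood pressure and heart rate measured after at least 3 minutes in each of two positions: "The supine measurements will be performed first, followed by standing". Table 3.7-1 schedules vital signs at baseline and at Weeks 1, 2, 3, 4, 8, 14, 18, 22 and 26; the telephone follow-up has none. Some visits may be virtual: "For the virtual visits, equipment will be provided to the caregiver with instructions for home use".

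Protocol 3.5.1 lists this item within the primary (safety) endpoint: "Change from baseline to postbaseline time points in 1) vital sign measurements".

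SAP 8.3 takes each position alone: "Measurements at different positions will be treated as different parameters for purposes of data analysis". It then closes the list: "Thus, there will be 7 parameters for the vital signs". For these it plans by-visit summaries of value and change from baseline, a last-visit summary, and an incidence table and listing of abnormal values. The listing shows "visit week, type of visit (virtual or in office), and dose at onset of the event if applicable".

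Under SAP Appendix 1 a reading is flagged if it lies beyond a fixed limit for age "and also represent a change from the subject's baseline value of at least the magnitude shown". The matching entry in the SAP 12 list of tables is "CT-11.2.2 Incidence of Potentially Clinically Relevant Abnormalities in Vital Signs (Safety Sample".

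**The concern.** A supine reading followed by a standing reading is a paired measurement, and what the pair adds is the difference between its members. The SAP never forms that difference. No variable, flag or table, including CT-11.1 to CT-11.2.3, gives standing minus supine within a visit or the number of subjects with a fall. The readings are used, but only one position at a time.

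At stake is a statement that the primary safety report should be able to make from data already collected: how many subjects had a measured postural fall on open-label treatment. If the single-position flags are read as a stand-in, the answer can be wrong in both directions.

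**Working it through.** **The plan's own count.** Temperature (1) plus SBP, DBP and heart rate (3) in two positions: 1 + 3 × 2 = 7. This agrees with SAP 8.3, and no postural difference is among the 7.

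**What the Appendix 1 rule can miss.** With low limit L, high limit H and change criterion c, a value v with baseline b is flagged if (v < L and b − v ≥ c) or (v > H and v − b ≥ c). If both readings of a pair lie within [L, H], neither can be flagged, whatever the baselines. A fall of exactly 15 mmHg is therefore never flagged when the supine value lies between L + 15 and H. Enumerating all baselines from 30 to 199 mmHg confirms this. The largest fall that can go unflagged with both readings in range is H − L.

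| Row | L–H (mmHg) | Supine range where a 15 mmHg fall is never flagged | H − L |
|---|---|---|---|
| SBP, 5 y | 80–115 | 95–115 | 35 |
| SBP, 6–9 y | 85–115 | 100–115 | 30 |
| SBP, 10–17 y | 90–120 | 105–120 | 30 |
| DBP, 5 y | 45–80 | 60–80 | 35 |
| DBP, 6–9 y | 50–80 | 65–80 | 30 |
| DBP, 10–12 y | 60–80 | 75–80 | 20 |
| DBP, ≥ 13 y | 60–85 | 75–85 | 25 |

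For example, at ages 10–17 with supine SBP 112, the SBP row cannot flag any fall from 15 up to 112 − 90 = 22 mmHg.

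**What the rule can flag without a postural fall.** At age 13–17, take SBP 105 supine and 105 standing at baseline, and 89 and 89 on treatment. Since 89 < 90 and 105 − 89 = 16 ≥ 15, both positions are flagged. The postural fall is 0.

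**How many falls chance alone would produce.** The documents give no SD for the standing-minus-supine difference, so this is a range under assumptions: mean 0, normal, independent across nine visits, SD 6, 8 or 10 mmHg. Per visit, p = P(Z ≥ 15/SD). At least one visit: 1 − (1 − p)^9. At least two: binomial with n = 9. Subject counts use the SAP 4 ceiling of 119.

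| SD (mmHg) | p | ≥ 1 of 9 visits | of 119 | ≥ 2 of 9 visits | of 119 |
|---|---|---|---|---|---|
| 6 | 0.0062 | 5% | 6 | 0.1% | 0.2 |
| 8 | 0.0304 | 24% | 29 | 3% | 3 |
| 10 | 0.0668 | 46% | 55 | 12% | 14 |

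These figures are for SBP only; counting DBP as well raises them. If a subject's visits are correlated at 0.3 to 0.5 (also assumed), the two-or-more figure rises from 2.9% to 5.4–6.1% at SD 8 and from 12% to about 14% at SD 10.

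**Visits that may be virtual.** Weeks 1, 3, 4, 8, 18 and 22 make 6 under Table 3.7-1. The COVID-19 addendum schedules add Weeks 2 and 14, making 8.

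**Cortisol row (separate, minor).** Appendix 2, in both documents, prints the AM entry as an interval, 6.7 to 22.60 ug/dL, and the PM entry as below 10 ug/dL. The ACTH row above it is written as below one value or above another. Taken literally as the flagging condition, an AM value of 12 is flagged while 3 and 30 are not.

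**The case against.** The strongest objection is that no stated requirement is missed. The endpoint is change from baseline, and SAP 8.3 delivers it for all 7 parameters. Protocol 7.6.3 asks for the incidence of abnormal vital signs, and CT-11.2.2 delivers that. This stands: the point is a gap in the analysis, not a departure from the protocol.

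Other outputs also cover part of the ground. Where the same subjects supply both readings, the mean postural difference at a visit can be worked out from the two means in CT-11.2.3. Investigators review the readings, and postural events reported as adverse events appear in the TEAE tables. That narrows the gap, but means do not give a number of subjects, and the other two routes depend on someone recognising and reporting the event.

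The proposed count is noisy: nine visits, no concurrent control, home equipment at some visits, and correlation within subjects that weakens the two-visit filter. This also stands. It is a reason to show how often and where each fall occurred, rather than to leave falls uncounted.

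The 15 mmHg cut-off is borrowed. In the addendum's Table 3.2-1, criterion 6, it is an entry exclusion for delayed rollover subjects and also has a symptoms limb. Its use here must be labelled as an analysis flag.

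On cortisol, the column heading and footnote make the intent clear, and SAP 8.2 does not name cortisol among its laboratory parameters. It remains a one-row drafting correction.

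**Conclusion.** The concern holds. As written, the SAP cannot report how many subjects had a measured postural fall, and the Appendix 1 flags can both miss falls and fire without one. The never-flagged ranges follow directly from the printed limits and need no assumption. How often the gap would matter in this trial cannot be estimated from the documents. The chance-finding figures rest on assumed SDs, a zero mean and independence across visits; they indicate how cautiously the new count should be read. This should be corrected because it concerns the primary safety endpoint and uses data already collected, but it breaches no stated requirement.

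**What to change.** In SAP 8.3:

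- Derive standing minus supine for SBP, DBP and heart rate at each visit, and summarise it by visit.
- Add an incidence table and a listing, by prior treatment group and overall, of subjects with a fall of at least 15 mmHg in SBP or DBP. Show any on-treatment occurrence and, separately, new onset relative to baseline. The separation is needed because under SAP 7.1 directly rolling-over prior-brexpiprazole subjects are already on drug at baseline.
- Show whether the fall occurred at one visit or more than one, and the visit type (virtual or in office), which 8.3 already lists for flagged values.
- State that the cut-off is the blood-pressure part of addendum criterion 6 without its symptoms limb, and that here it is an analysis flag only, not a clinical rule.

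Separately, rewrite the cortisol row of Appendix 2 in the SAP and the protocol with out-of-range operators, as in the ACTH row.

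The cost is three derived variables, one summary, one incidence table, one listing and one rewritten row, with no new measurements. The drawback is that some counted falls will be chance; the one-visit/several-visit split and the visit type let the reader judge this.

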8.4 Electrocardiogram Data

Electrocardiogram (ECG) measurements will be made in office at 2 specified visits (Weeks 14 and 26 visits) during the open-label treatment period. The standard 12-lead measurements include QTc, heart rate, PR interval, and QRS complex. For the analysis of QT and QTc, data from three consecutive complexes (representing three consecutive heart beats) will be measured to determine average values. The following QT corrections will be used for reporting purposes:

- 1) QTcF is the length of the QT interval corrected for heart rate by the Fridericia formula: $QTcF = QT/(RR)^{0.33}$
- 2) QTcN is the length of the QT interval corrected for heart rate by the FDA Neuropharm Division formula: $QTcN = QT/(RR)^{0.37}$.

For each of the quantitative ECG parameters, assessment value and change from baseline value will be summarized on the OC data for each of the specified visits above, as well as

on the LOCF data for the last assessment visit, by using descriptive statistics for continuous variables.

Criteria for identifying potentially clinically relevant ECG abnormality for subjects of 5 to 17 years of age are provided in Appendix 3. All potentially clinically relevant ECG abnormalities during the open-label treatment period will be listed by prior treatment group, patient number, sex, age, body weight, baseline value, visit, description of the findings, and dose at onset of the event if applicable. In addition, the number and percentage of patients who had a potentially clinically relevant ECG abnormality will be tabulated by prior treatment group based on the observation at the scheduled and the unscheduled (if any) post-baseline visits.

Categorical Change in ECG parameters during the open-label treatment period will be summarized based on the following criteria:

| Table 8.4-1 | Categorical Change Criteria in QT/QTc Parameters | |
|--------------------|---|--|
| Classification | Category | Criteria |
| QT | New onset (≥ 450 msec for men or ≥ 470 msec for women) | New onset in QT means a subject who attains a cut off value during treatment period but not at baseline. |
| QTc ^a | New onset (≥ 450 msec for men or ≥ 470 msec for women) | New onset in QTc means a subject who attains a cut- off value during treatment period but not at baseline. |
| | New onset (≥ 450 msec for men or ≥ 470 msec for women) and $> 10\%$ increase | New onset and > 10% increase in QTc means a subject who attains a cut off value and > 10% increase during treatment period but not at baseline |
| | New onset (> 500 msec) | New onset (> 500 msec) in QTc means a subject who attains a value > 500 msec during treatment period but not at baseline. |
| | Increase 30 - 60 msec | Increase from baseline value > 30 and ≤ 60 msec in QTc. |
| | Increase > 60 msec | Increase from baseline value > 60 msec in QTc. |

^aQTc categorical change criteria apply to QTcF and QTcN.

8.5 Physical Examinations

By-subject listings will be provided for physical examinations (PE), which is scheduled at the end (ie, the Week 26 visit) of the open-label treatment period, following the screening/baseline visit.

8.5.1 Body Weight, Waist Circumference and BMI

Measurements on body weight, waist circumference and height will be collected at two specified visits (ie, Weeks 14 and 26) in office at clinical site during the open-label treatment period. For each visit, BMI will be derived as: weight in kilograms divided by the square of height in meters.

Measurement value and change from baseline value at each of the two specified visits above during the open-label treatment period in each of the above-mentioned four parameters will be summarized on the OC data by using descriptive statistics for continuous variables. Likewise, the summary statistics will also be computed on the LOCF data for the last visit.

Number and percentage of subjects having had significant weight gain (\geq 7% increase in body weight relative to baseline) and significant weight loss (\geq 7% decrease in body weight relative to baseline) during the open-label treatment period will be respectively tabulated by visit and for the overall treatment period as well.

8.5.2 Z-score

Z-score is a variable of interest to be derived due to the natural growth of children and adolescent subjects. Weight z-score describes how similar a subject is to his/her age and gender peers by determining the number of standard deviations from the expected weight. For each scheduled visit, weight z-score is calculated as the deviation of the subject's weight from the mean weight of the reference population divided by the standard deviation for the reference population. Weight z-score and change from baseline in weight z-scores will be summarized on the OC data by specified visit (ie, Weeks 14 and 26) and the last visit by using descriptive statistics for continuous variables.

Height z-score and BMI z-score will be similarly calculated and similarly summarized as that for weight, based on the OC data and last visit. Refer to Section 8.5.2.1 for the calculation of z-score for body weight, height, and BMI. Furthermore, the number and percentage of subjects with the magnitude of change being ≥ 0.5 or ≤ -0.5 in BMI z-score (relative to baseline) will be tabulated on the OC data by specified visit (ie, Weeks 14 and 26) and the last visit.

8.5.2.1 Calculation of Z-scores for Body Weight, Height, and BMI

Age and gender adjusted z-scores for body weight, height and BMI will be calculated using the approach of the Center for Disease Control and Prevention (CDC), USA. The CDC provides a reference dataset (CDCref_d.sas7bdat in sas data format or CDCref_d.csv in csv data format) and a SAS program (cdc-source-code.sas) along with detailed instructions for the calculations³.

Z-scores are calculated as Z = [((value / M) ** L) - 1] / (S * L), in which "value" is the child's BMI, weight, height, etc. The L, M, and S values are in the reference dataset and vary according to the child's sex and age. The following rules will be observed:

- 1) Age (in months) at the day of assessment, which is an input for the calculations, will be calculated as: (assessment date birth date + 1)/(365.25/12).
- 2) In principle, BMI and its z-score will be calculated only if weight and height are both taken on the same day.
- 3) The above calculations are applicable in children and adolescents older than 24 months but younger than 20 years of age.

It is not anticipated that CDC's information (including the reference dataset or the SAS program or the instructions for the calculations) will be updated in the short run. Nevertheless, the information at the CDC website will be re-checked for any updates within a month prior to the final database lock, and updated information will be used if any.

8.6 Extrapyramidal Symptoms Rating Scales (SAS, AIMS and BARS)

Extrapyramidal symptoms scales (SAS, AIMS and BARS) will be assessed in office at clinical site at three specified visits (Weeks 2, 14 and 26) during the open-label treatment period. The SAS total score, the AIMS total score, and the BARS global clinical assessment score (see Section 11.5, Section 11.6, and Section 11.7 for the construction of these scores) and the change from baseline in these scores will be respectively summarized on the OC data by visit above and on the LOCF for last visit by using descriptive statistics for continuous variables. For the AIMS individual item score on Item 8, 9 and 10, summary statistics will be computed analogously to the above.

In addition, incidence of BARS global clinical assessment during the open-label treatment period by severity category will be provided using summary statistics on OC data and last visit.

